3.3 Study Duration and Dates

Overall duration of the study is approximately 18 months. This includes up to a 1-month screening period, followed by an enrollment period of up-to 6 months. Each subject in both treatment groups will complete a 6-month primary evaluation period. Residual implant assessment will be performed on Day 8 and at Months 1, 2, 3, 4, 5, and 6, and if necessary at monthly visits thereafter until the subject requires retreatment, or to 1 month after the implant is no longer visible, or to Month 9, whichever comes first.

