At these visits, the subject will be queried regarding any changes to their ocular or medical health status since the previous visit, and also if there have been any changes to their ongoing medications or procedures. Vital signs (heart rate and blood pressure) will be collected. Blood samples will be collected (Month 1 and Month 2 visits only) for laboratory assessment of clinical chemistry and hematology.

The following assessments will be conducted OU:

- BCVA by ETDRS will be conducted following manifest refraction
- Slit-lamp biomicroscopy
- IOP measured using a Goldmann applanation tonometer

Following mydriasis, the following procedures will be performed OU, unless otherwise specified:

- SD-OCT (study eye)
- Fundus examination
- The implant will be viewed to verify its status. (study eye)

7.2.4 Visit 6 ([REDACTED] ± 3 Days) and Visit 9 ([REDACTED] ± 3 Days) Procedures

At these visits, the subject will be queried regarding any changes to their ocular or medical health status since the previous visit, and also if there have been any changes to their ongoing medications or procedures. Vital signs (heart rate and blood pressure) will be collected.

Blood samples will be collected for laboratory assessment of clinical chemistry and hematology and if the subject is a female of child-bearing potential, a urine pregnancy test should be administered (Visit 9 only).

The following procedures will be conducted OU:

- BCVA by ETDRS will be conducted following manifest refraction
- Slit-lamp biomicroscopy examination
- Gonioscopy (study eye)
- IOP measured using a Goldmann applanation tonometer

Following mydriasis, the following procedures will be performed OU unless otherwise noted:

- SD-OCT (study eye)
- Fundus examination (study eye)
- Fluorescein angiography
- 3-field fundus photography (study eye)
- The implant will be viewed to verify its status (study eye)

If residual implant is still visible in the vitreous at the Month 6 visit, the subject will be required to return to the site at Month 7 for safety follow-up. Otherwise, the Month 6 visit will be the final visit, and the subject should be thanked for their participation in the study.

7.3 [REDACTED] or Early Termination Procedures

Procedures that should be conducted in the event that the subject needs to exit the study prior to Month 6 (Visit 9) are provided above in Section [7.2.4](#).

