7.4 Follow-up Visits ([REDACTED] ± 3 days as required for residual implant assessment)

Monthly safety visits should be scheduled if, following the assessments at Month 6 (Visit 9) are completed, it is noted that the vitreous still contains visible implant. At these visits, the subject will be queried regarding any changes to their ocular or medical health status since the previous visit, and also if there have been any changes to their ongoing medications or procedures. Vital signs (heart rate and blood pressure) will be collected.

The following procedures will be conducted OU:

- BCVA by ETDRS following manifest refraction
- Slit-lamp biomicroscopy examination
- IOP measured using a Goldmann applanation tonometer

Following mydriasis, the following procedures will be performed in the study eye:

- SD-OCT
- Fundus examination
- 3-field fundus photography
- The implant will be viewed to verify its status

If necessary, a second follow-up visit will be scheduled. The format of this follow-up visit should continue until either the subject requires re-treatment (i.e. standard of care rescue treatment), or until 1 month after no residual implant is observed, or to Month 9, whichever comes first, at which point the subject will exit the study.

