2.2 Secondary Variables

The secondary variables are related to efficacy and include the following:

- BCVA by ETDRS method
- CRT as assessed by SD-OCT
- Area of non-perfusion and area of leakage as assessed by fluorescein angiography (FA) and 3-field fundus photography (FP)
- Percentage of subjects receiving rescue therapy overall

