A linear model with change from baseline BCVA letters for study eye only as the response, baseline BCVA letters as a covariate, and treatment group as a main effect will be fit to determine treatment group effect with separate models completed for each follow-up visit. These analyses will be used to determine differences in formulations and may be used to assess whether there are differences in outcomes between subjects' data pre- and post-interim to determine whether the data may be pooled. Subjects who receive rescue medication prior to the summarized visit will have their measure replaced with their last observation prior to receiving rescue medication. The least squares mean, standard error, and CI for each treatment group, and the difference between treatment groups will be presented for

study eye only. Additionally, analyses will be completed using individual two-sample t-tests and 90% and 95% CIs around the difference between treatment groups in mean BCVA and mean change from baseline BCVA for study eye only.

Median time (in months) to achieve a treatment response of ≥ 15 letters improvement from baseline in BCVA for study eye and median time (in months) to rescue therapy will be estimated using Kaplan-Meier methods with 90% and 95% CI, calculated using the method of Brookmeyer and Crowley (1982). The log rank statistic will be used to determine differences in time to achieve response between the two treatment groups to determine differences in formulations. Cox proportional hazards will also be used to analyze time to event, including baseline BCVA as a covariate. Results from unscheduled visits or early termination visits will be included in the time to event analysis.

For the event of achieving a treatment response of ≥ 15 letters improvement from baseline in BCVA for study eye, the starting date will be the date of first dose. Subjects receiving rescue medications prior to or on the same date as the achievement of improvement will be considered censored on the day of rescue medication receipt; subjects with neither rescue medications received nor improvement achieved will be considered censored on the last date known to be rescue medication free and improvement achievement free. For the event of receiving rescue therapy, the starting date for the time to event evaluation will be the date of first dose. Subjects who do not receive rescue therapy will be considered censored on the last date known to be event free.

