13.2 SD-OCT, FA and FP

CRT measured by Cirrus (Zeiss) or Spectralis (Heidelberg) instrument will be summarized at each visit, using continuous summary statistics including change from baseline. Comparison between treatment groups for CRT will be performed using the same approaches as specified for BCVA in section 13.1.

Two time to event analyses for CRT of study eye as specified below will be evaluated using the same statistical method for the event of achieving a treatment response of ≥ 15 letters improvement from baseline in BCVA in section 12.1. The starting date of the evaluation will be the date of first dose. Results from unscheduled visits or early termination visits will be included in the time to event analysis.

- Time to resolution of macular edema: defined as first time point at which CRT is less than or equal to 315 μm for study eye.
- Time to loss of resolution of macular edema among treatment responders (population for this analysis includes subjects who achieved resolution of macular edema except on the last day of measurement): defined as first time point at which CRT returns to greater than 315 μm from first achieving the resolution of macular edema.

For the event of resolution of macular edema, subjects receiving rescue medication prior to or on the same date as the achievement of resolution of macular edema will be censored on the day of their rescue medication receipt. Subjects with neither rescue medications received, nor resolution of macular edema will be considered censored on the last date known to be rescue medication free and resolution of macular edema free. For the event of loss of resolution of macular edema after resolution achieved, subjects receiving rescue medications prior to the loss of resolution of macular edema will be considered censored on the day of rescue medication receipt and subjects receiving rescue medications on the same date as loss of macular edema will be considered for loss of macular edema. Subjects with neither loss of resolution of macular edema nor rescue medication received will be considered censored on the last date known to be loss of resolution of macular edema free and rescue medication free.

Total area of capillary non perfusion within ETDRS Grid (16DA) and total area of fluorescein leakage within the ETDRS grid assessed by FA using both Optos instruments (i.e ultra-widfield) and non-Optos (i.e widefield) will be summarized using continuous summary statistics.

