15.5 Clinical Laboratory Data

The observed and change from baseline values of hematology and clinical chemistry parameters will be summarized, overall and by treatment group, at each visit with continuous descriptive statistics. Normal ranges will be used to determine the classifications. Values below the normal range will be classified as low normal, low panic, values above the normal range will be classified as high normal and high panic, and values within the normal range will be classified as normal. Analyses will also include shifts from baseline to each post-baseline visit using low normal, and high classifications.

Subject listings will be provided for hematology and clinical chemistry separately and will include a column to distinguish abnormal values.

16. Interim Analyses

An interim analysis may be conducted when the first 20 subjects enrolled in the randomized phase complete their Month 6 visit or discontinued the study. Safety, tolerability, and efficacy data will be reviewed during this interim analysis to assist in planning of future studies. A final analysis will be performed when all randomized subjects in each treatment group have completed the Month 6 visit.

17. Changes from Protocol-Stated Analyses

1. Comparison between treatment groups for CRT will be performed as specified in Section 12.2.
2. Two time to event analyses for CRT will be performed as specified in Section 12.2.
3. No analyses will be performed for CFT.
4. Discrete summary statistics for patient receiving rescue therapy will be removed.

18. References

Brookmeyer, R. and Crowley, J. (1982) A confidence interval for the median survival time. *Biometrics* 1982; 38: 29-41.

19. Revision History

Summary of Changes

Section #	Description of Change
List of Abbreviation	More abbreviation terms added
8.2.1	Missing/partial dates for AEs handling added
8.2.2	Missing/partial dates for concomitant medication handling added
8.3	Baseline definition updated
9	COVID-19 related discontinuation and protocol deviation added to subject disposition summary and COVID-19 related protocol deviation listing added
12	Implant residual assessment added
13.1	1. Boxplot of change from baseline in BCVA letter score for study eye added for subject groups with gain of ≥ 15 letters, ≥ 10 letters, and ≥ 5 letters 2. More details for the event of receiving rescue therapy added

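### Time to rescue has no Month 6 cut-off, so its curve and possibly its median can run into Months 7–9, where only eyes with implant visible at Month 6 are followed

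*SAP*

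**What the plan says.** - **Event and censoring.** SAP 13.1 measures time to rescue from first dose, counts rescue received, and reports a Kaplan-Meier median with 90% and 95% CIs. For everyone else: "Subjects who do not receive rescue therapy will be considered censored on the last date known to be event free". No horizon is given there, in SAP 16 or 17, or in the title of Table 14.2.3. By contrast, SAP 13 ties the visit-based BCVA and CRT endpoints to Months 1 to 6.
- **When the analysis is run.** SAP 16: "A final analysis will be performed when all randomized subjects in each treatment group have completed the Month 6 visit". This sets when the analysis happens. It does not truncate the data of subjects who entered early. Protocol 3.3 describes a screening period "followed by an enrollment period of up-to 6 months".
- **Who is followed after Month 6.** Under Protocol 7.2.4, subjects with visible implant at Month 6 return at Month 7. "Otherwise, the Month 6 visit will be the final visit".
- **How that follow-up ends.** Protocol 7.4 continues monthly visits "until either the subject requires re-treatment (i.e. standard of care rescue treatment), or until 1 month after no residual implant is observed". Month 9 is the latest end point, and the subject leaves the study once any of these is met. At these visits subjects are asked "if there have been any changes to their ongoing medications or procedures". Protocol 6.9 has medications taken during the study recorded. Nothing provides for capturing rescue given after exit.
- **Other rescue reporting.** SAP 2.2 still lists "Percentage of subjects receiving rescue therapy overall", but SAP 17 removes the discrete rescue summaries. Table 14.2.3 is the only table in SAP 20 dedicated to rescue.

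**The concern.** A curve with no stated horizon uses whatever follow-up exists. Here, follow-up beyond Month 6 depends on a post-treatment finding, visible implant. Kaplan-Meier treats eyes censored at Month 6 as if they had the same later risk as those still followed. For an eroding drug implant that is doubtful, although the documents offer no rescue rates by implant status.

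There is also a mismatch between the event and the exit rule. The SAP counts rescue *received*, while Protocol 7.4 ends follow-up when re-treatment is *required*. If treatment is given after exit, or is not recorded by the exit visit, the eye is censored on the day it fails. That censoring is informative and lengthens the apparent time without rescue. The same can happen at Visit 9, the last visit for every eye without visible implant.

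What is at stake is how Table 14.2.3 is read. Protocol 3.2 wants a long duration of effect, and the results are meant to inform later designs. A median that falls in Months 7–9 would look like a whole-group durability figure but would rest on a subset.

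**Working it through.** **Plan figures.** The documents give no expected rescue rate, residual-implant share or exit timing, so there is no plan figure for rescue to reproduce. The only sample-size figure is the 13.9% adverse-event bound for 20 subjects (Protocol 9.2, SAP 5). It reproduces as 1 − 0.05^(1/20) = 0.139 and has no bearing here beyond fixing the arm size at 20. All rescue inputs below are assumptions.

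**Step 1. Can Month 7–9 data exist at the final analysis?** Assume enrolment takes the full 6 months. The last Month 6 visit then falls at about study month 6 + 6 = 12. A subject treated by month 12 − 7 = 5 can have Month 7 data, and one treated by month 12 − 9 = 3 can have Month 9 data. Faster enrolment shrinks this.

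**Step 2. Effect of recording.** Assume 20 eyes with no dropout, and 5 rescued by Month 6, so S(6) = 15/20 = 0.75. Of the 15 unrescued eyes, 7 have no visible implant and are censored at Month 6; 8 are followed. No eye leaves because its implant has gone before Month 8. Each event multiplies S by (1 − 1/number at risk), with events before censorings at ties. Two eyes exit needing re-treatment, at Months 7 and 8.
- Both recorded as rescued: S(8) = 0.75 × 7/8 × 6/7 = 0.5625.
- Only the first recorded: 0.75 × 7/8 = 0.656.
- Neither recorded: 0.75.

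Now add a third such exit at Month 9, with 0, 1 or 2 eyes having left at Month 8 because the implant had gone.
- All recorded: 0.5625 × 5/6 = 0.469, × 4/5 = 0.450, or × 3/4 = 0.422. The median is Month 9 in each case.
- None recorded: 0.75, and the median is not reached.

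Varying the number followed, with two recorded exits:
- 10 eyes: 0.75 × 9/10 × 8/9 = 0.600, against 0.75 if unrecorded.
- 4 eyes: 0.75 × 3/4 × 2/3 = 0.375, against 0.75 if unrecorded.

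**Step 3. Effect of selection.** Assume S(6) = 0.70. Let p be the share of unrescued eyes with visible implant, h1 their monthly rescue risk and h0 that of the other eyes. Over Months 7–9:
- Whole-group value: S(9) = 0.70 × [p(1 − h1)³ + (1 − p)(1 − h0)³].
- Kaplan-Meier from followed eyes, all rescues recorded: 0.70 × (1 − h1)³.

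With h1 = 0.10, Kaplan-Meier gives 0.70 × 0.729 = 0.510. The whole-group value is:
- h0 = 0.10: 0.510, so no bias.
- h0 = 0.20: 0.404 (p = 0.3) or 0.434 (p = 0.5).
- h0 = 0.30: 0.321 (p = 0.3) or 0.375 (p = 0.5).

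If only half the re-treatments are recorded, Kaplan-Meier gives 0.70 × 0.95³ = 0.600; if none are, 0.70. If h0 were below h1, the selection bias would run the other way.

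**Step 4. The same gap at Visit 9.** With 5 rescues recorded, suppose one more eye is found at Visit 9 to need rescue and is treated after leaving. The Month 6 estimate stays at 15/20 = 0.75; counting that eye gives 14/20 = 0.70.

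**Step 5. When nothing changes.** The tail does not matter if no eye has residual implant or if the curve stops at Month 6. The recording effect vanishes if every rescue is recorded by exit. If 11 or more of 20 eyes are rescued by Month 6, S(6) is at most 9/20 = 0.45 and the median lies at or before Month 6 regardless. At exactly 10, S(6) = 0.50 and the answer depends on the median convention.

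**The case against.** The strongest reply is that no decision depends on the tail. Protocol 3.1 bases formulation selection on data through Month 6, the study is not powered for efficacy, and the log-rank sentence in SAP 13.1 names time to response, not time to rescue. This stands. A reader might infer that the choice between CF1 and CF2 is compromised; the documents do not support that.

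Second, censoring at failure is hypothetical. Protocol 7.4 equates re-treatment with standard-of-care rescue and asks about medications and procedures at each visit, so rescue given and recorded by the exit visit counts as an event. This also stands. A reader might infer that every re-treatment exit is censored as a non-event; the documents do not say so. Nor do they say that rescue is given before exit, and the eCRF and Manual of Procedures are not available.

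Third, a shrinking late risk set is ordinary in Kaplan-Meier, and equal risks give no selection bias (Step 3). That is true, but here the risk set shrinks by implant status, and nothing tells a reader of Table 14.2.3 so. The per-visit implant summary (SAP 12, Table 14.1.5) shows how many eyes still have implant, but not how many are at risk of rescue.

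Fourth, other outputs bear on durability and rescue use. "Time to loss of resolution of macular edema among treatment responders" in SAP 13.2 covers only eyes whose CRT had resolved. Rescue drugs would appear in the ocular concomitant medication table, but without a time-to-event estimate. The removal of the discrete rescue summaries is a declared change and a separate matter.

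**Conclusion.** The point holds as a modest, inexpensive improvement. SAP 13.1 leaves the horizon of time to rescue open, and the protocol restricts follow-up after Month 6 to eyes with implant visible at that visit. Any Month 7–9 segment, and a median falling there, therefore describes a selected group.

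Two conditions decide whether it misleads. Selection bias needs rescue risk to differ by implant status. Overstatement from the exit rule needs re-treatment exits without rescue recorded by exit. Neither can be settled from the documents, so the size is unknown. The illustrations run from no difference to 0.375 against 0.75, and every input except the arm size is assumed.

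It would also be too strong to conclude that estimates through Month 6 are immune: an eye found to need rescue at Visit 9 and treated after leaving is missed in the same way. A Month 6 cut-off removes the selected tail from the main estimate but does not by itself close that gap.

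**What to change.** In SAP 13.1:
1. Censor the main time-to-rescue analysis at the Visit 9 (Month 6) date, or at the last event-free date if earlier. Count rescue given on the Visit 9 date as an event.
2. Report the Month 6 Kaplan-Meier estimate with 90% and 95% CIs beside the median.
3. Use one event definition throughout, with rescue received as the main event. Add a sensitivity analysis that also counts re-treatment required at study exit, whether at Visit 9 or later, as an event on that date.
4. Show any Month 7–9 curve only as supplementary, with numbers at risk and a note that only residual-implant eyes are followed.

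The rules for offering rescue do not change.

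**Cost.** The main analysis needs SAP wording and one date cut-off in programming. The sensitivity analysis needs a recorded judgement at exit that re-treatment is required; the eCRF is not among the documents, so this may already be collected.

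**Downsides.** The median will not be reached unless about half the eyes are rescued by Month 6, which is why the Month 6 estimate is needed beside it. The sensitivity event rests on open-label investigator judgement.

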13.2 SD-OCT, FA and FP

CRT measured by Cirrus (Zeiss) or Spectralis (Heidelberg) instrument will be summarized at each visit, using continuous summary statistics including change from baseline. Comparison between treatment groups for CRT will be performed using the same approaches as specified for BCVA in section 13.1.

Two time to event analyses for CRT of study eye as specified below will be evaluated using the same statistical method for the event of achieving a treatment response of ≥ 15 letters improvement from baseline in BCVA in section 12.1. The starting date of the evaluation will be the date of first dose. Results from unscheduled visits or early termination visits will be included in the time to event analysis.

- Time to resolution of macular edema: defined as first time point at which CRT is less than or equal to 315 μm for study eye.
- Time to loss of resolution of macular edema among treatment responders (population for this analysis includes subjects who achieved resolution of macular edema except on the last day of measurement): defined as first time point at which CRT returns to greater than 315 μm from first achieving the resolution of macular edema.

For the event of resolution of macular edema, subjects receiving rescue medication prior to or on the same date as the achievement of resolution of macular edema will be censored on the day of their rescue medication receipt. Subjects with neither rescue medications received, nor resolution of macular edema will be considered censored on the last date known to be rescue medication free and resolution of macular edema free. For the event of loss of resolution of macular edema after resolution achieved, subjects receiving rescue medications prior to the loss of resolution of macular edema will be considered censored on the day of rescue medication receipt and subjects receiving rescue medications on the same date as loss of macular edema will be considered for loss of macular edema. Subjects with neither loss of resolution of macular edema nor rescue medication received will be considered censored on the last date known to be loss of resolution of macular edema free and rescue medication free.

Total area of capillary non perfusion within ETDRS Grid (16DA) and total area of fluorescein leakage within the ETDRS grid assessed by FA using both Optos instruments (i.e ultra-widfield) and non-Optos (i.e widefield) will be summarized using continuous summary statistics.

Change in fluorescein leakage from Screening within the ETDRS Grid (16DA) assessed by FA will be summarized using discrete summary statistics including change from baseline.

Separate subject listings of SD-OCT and FA results will be produced.

Box plot of change from baseline in CRT for study eye only will be presented.

Line plot of CRT for study eye will be prepared with visit on x-axis and mean change from baseline in CRT withon y-axis by treatment group.

14. Exploratory Analyses

There are no exploratory analyses planned for this study.

15. Safety Analyses

All safety analyses will be conducted using the Safety population.

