4. STUDY POPULATION SELECTION

4.1 Study Population

4.2 Inclusion Criteria

Subjects MUST meet all of the following criteria at the screening and baseline visits to enter into the study:

1. At least 18 years of age
2. Vision-loss attributed to clinically detectable ME associated with either CRVO or BRVO. Subjects may be treatment-naïve, or if previously-treated with a steroid, must have demonstrated response to treatment.
3. Duration of ME (defined as the time since initial diagnosis of ME) ≥ 9 months in subjects with CRVO and ≥ 12 months in subjects with BRVO. If both eyes are eligible, the study eye will be the eye with worse VA
4. Best-corrected visual acuity (BCVA) as measured by the ETDRS methodology of between 25 and 70 letters (+1.2 and +0.3 logMAR units or 20/320 and 20/40 Snellen equivalent) in the study eye
5. Retinal thickness in the central subfield (as measured by SD-OCT) of >290 μm (females) and >305 μm (males) if using a Cirrus (Zeiss) instrument, or if a Spectralis (Heidelberg) instrument is used, thickness should be >305 μm (females) or >320 μm (males) in the study eye
6. Be able to understand and willing to provide written informed consent
7. Be willing and able to adhere to the instructions set forth in the study protocol

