6.6 Efficacy Assessments

Best Corrected Visual Acuity (BCVA) will be assessed by the ETDRS method. Subjects will have their visual acuity measured in a 4-meter lane under standard illumination by a certified examiner reading a standard ETDRS chart. Subjects will undergo manifest refraction for each BCVA evaluation at each visit. The visual acuity lane will be certified, as will the visual acuity examiner prior to study initiation. Exact specifications for the visual acuity lane, illumination, charts, light box and refraction lens are detailed in the MoP.

Efficacy will be assessed by evaluating the following (see Statistical Analysis Plan [SAP] and MoP for details):

- BCVA by ETDRS method
- Central Retinal/Foveal Thickness (CRT/CFT) as assessed by SD-OCT (Heidelberg or Zeiss instruments – see Section 4.2 and MoP)
- Fluorescein Angiography and Fundus exam
- Percentage of subjects requiring rescue therapy overall and by visit

Other secondary efficacy analyses may be carried out as described in the study SAP.

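### One 315 µm cut-off defines resolution and loss of resolution on both Cirrus and Spectralis, although the protocol's own entry limits put the two devices 15 µm apart

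*SAP*

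**What the plan says.** Inclusion criterion 5 (Protocol 4.2, repeated in the synopsis) sets the minimum central subfield thickness by device and sex. For Cirrus it is ">290 μm (females) and >305 μm (males) if using a Cirrus (Zeiss) instrument". For Spectralis, "thickness should be >305 μm (females) or >320 μm (males) in the study eye".

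Either device may supply the efficacy measurement. Protocol 6.6 lists central thickness "as assessed by SD-OCT (Heidelberg or Zeiss instruments", and refers to Section 4.2 and the Manual of Procedures.

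SAP 13.2 puts both devices into one CRT summary ("CRT measured by Cirrus (Zeiss) or Spectralis (Heidelberg) instrument will be summarized at each visit") and one group comparison: "Comparison between treatment groups for CRT will be performed using the same approaches as specified for BCVA in section 13.1". It also adds two time-to-event analyses. Resolution of macular edema is "defined as first time point at which CRT is less than or equal to 315" µm. Loss of resolution is "defined as first time point at which CRT returns to greater than 315" µm after resolution was first reached. Neither definition mentions the device.

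The SAP contains no conversion between devices, no CRT table by device, no device term or stratum, and no rule that an eye must stay on one device. The example code in SAP 13.1 compares treatments in the log-rank test with no other stratum, and the Cox model holds baseline BCVA and treatment only.

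**The concern.** The protocol does not use one thickness limit for both devices at entry, but the SAP uses one at follow-up. If Cirrus reads 15 µm lower than Spectralis, as the entry limits imply, the same retina can be resolved on one instrument and unresolved on the other. An absolute threshold has no baseline subtraction to remove the offset.

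The two analyses describe how many eyes dry out, how fast, and for how long. Protocol 3.1 says that safety data and efficacy signals through Month 6 will guide the choice of formulation. Protocol 3.2 names long duration of effect as a property of the optimal formulation. The device is likely to be a feature of the site, and about 40 randomized eyes are spread over about 20 sites, so the device mix may differ between arms by chance. A resolution rate carried into the design of a later study would also depend on this trial's device mix.

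**Working it through.** The plan states no figure for the device effect, so the check starts from the entry limits.

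**Step 1. Device gap from criterion 5.** Women: 305 − 290 = 15 µm. Men: 320 − 305 = 15 µm. The gap is the same in both sexes.

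**Step 2. Which readings are affected.** Take the gap as a constant offset, so that Cirrus = Spectralis − 15 µm. An eye is resolved on Spectralis if its Spectralis value X is at most 315. It is resolved on Cirrus if X − 15 is at most 315, that is, if X is at most 330. Only eyes with X above 315 and up to 330 change status. Those eyes read above 300 and up to 315 on Cirrus.

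**Step 3. Share of eyes affected at one visit.** The documents give no follow-up CRT distribution. Assume X is normal on the Spectralis scale with mean μ and SD σ. The affected share is Φ((330 − μ)/σ) − Φ((315 − μ)/σ).

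| Mean (µm) | SD 60 | SD 90 | SD 120 |
|---|---|---|---|
| 300 | 9.3% | 6.4% | 4.9% |
| 320 | 9.9% | 6.6% | 5.0% |
| 350 | 9.0% | 6.3% | 4.9% |
| 380 | 6.3% | 5.4% | 4.4% |

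- Largest cell (320, 60): Φ(0.167) − Φ(−0.083) = 0.566 − 0.467 = 0.099.
- Smallest cell (380, 120): Φ(−0.417) − Φ(−0.542) = 0.338 − 0.294 = 0.044.

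**Step 4. Effect on a reported rate.** Suppose 315 µm is a Spectralis value and half the eyes are on Cirrus (an assumption). The pooled share resolved at a visit is then too high by half the Step 3 figure: 0.5 × 4.4 = 2.2 points to 0.5 × 9.9 = 5.0 points.

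**Step 5. Effect on the comparison of formulations.** Let one arm of 20 have 5 more Cirrus eyes than the other. The between-arm difference in the share resolved moves by (5/20) × 0.044 = 0.011 to (5/20) × 0.099 = 0.025, or 1.1 to 2.5 points. The upper figure is 0.025 × 20 = half an eye. The sampling standard error of that difference near 50% is √(2 × 0.5 × 0.5/20) = 0.158, about 16 points.

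**Step 6. How likely such an imbalance is.** If each eye has a 50% chance of being on Cirrus, two independent binomial counts of 20 differ by 5 or more with probability 15%. If exactly 20 of the 40 eyes are on Cirrus, the hypergeometric probability is 11%. Both assume allocation not stratified by device.

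These are single-visit figures. Both endpoints are first crossings over repeated visits, so an eye that stays near the cut-off can be affected more than once. I have not quantified that.

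**The case against.** The strongest reply is that the effect on the choice of formulation is slight. That stands. Allocation is 1:1, so device mix is balanced in expectation. Part of Protocol 5.4 is redacted, so stratification by device cannot be ruled out. Even a 5-eye imbalance moves the comparison by far less than its standard error. A reader might infer that the instrument decides whether eyes resolve, or that it biases one formulation against the other. The documents support neither: only eyes near the cut-off are affected, and the consequence is mainly shifted rates and added noise.

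A second reply is that instrument detail belongs to the Manual of Procedures and that a Reading Center is used, so readings may already be converted. This also stands in part: SAP 13.2 does not say that the values are unconverted. But neither document says that they are converted, and the SAP would still need to name the scale of its cut-off.

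Third, the CRT endpoint listed in Protocol 9.6.1 is change from baseline, where a constant offset cancels if the eye stays on one device. That is right, so the point does not reach those means. Nothing in the documents suggests that eyes switch devices, though nothing visible forbids it.

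Fourth, criterion 5 is an entry limit and not a definition of edema. A reader might note that 315 µm is 25 µm above the entry limit for a woman on Cirrus and 5 µm below it for a man on Spectralis, and conclude that resolution must follow the sex-specific limits too. The documents do not support that step. Detectable edema is a separate requirement in criterion 2, nothing says that resolution must mirror entry, and no reason is given for the sex difference.

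Last, these are secondary analyses in a study that is not powered for efficacy. That limits the weight of the point but does not remove the inconsistency.

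**Conclusion.** The point holds for the two 315 µm time-to-event endpoints and, for the same reason, for summaries of absolute CRT. As written, the SAP applies one number to two scales that the protocol separates by 15 µm, and does not say which scale the number is on.

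The single-visit sizes in the working depend on the assumed normal follow-up distribution and on reading the entry-limit gap as a constant device offset. The 15 µm gap comes from the protocol; its use as a calibration constant is an approximation. The primary safety objective is untouched. The change is worth making because it is cheap and the rates may be carried into later studies, not because the formulation comparison is likely to be reversed.

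**What to change.** In SAP 13.2:

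1. State which device scale 315 µm refers to. If the Manual of Procedures or the Reading Center already converts readings, say so; item 2 is then met.
2. Otherwise make one correction only, and apply it to both time-to-event endpoints and to absolute CRT summaries. Either use device-specific cut-offs 15 µm apart (315 µm on Spectralis and 300 µm on Cirrus if 315 µm is a Spectralis value; 330 µm and 315 µm if it is a Cirrus value), or convert all CRT to one scale and keep a single cut-off. Doing both would correct twice.
3. As a sensitivity analysis, stratify the log-rank and Cox analyses of these two endpoints by device. Stratifying alone does not repair the definition. A device term in the change-from-baseline model is not needed for this purpose, because a constant offset already cancels there.
4. Flag any eye whose device changes during follow-up.

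Sex-specific resolution limits are optional and not part of this correction.

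The cost is a few sentences, a device variable in the analysis data, one derived variable, and a stratified rerun of two analyses. The downsides are that 15 µm is only an approximate offset and that stratifying about 40 eyes loses a little information.
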